**Protocol 01**

**06/16/2014**

## A. STUDY AIMS

Specific Aim 1: To determine if routine dietary supplementation with enteral tube feeding affects recovery and quality of life after esophagectomy. Medicare rules only pay for enteral supplements (tube feeding) if the patient needs alternative feeding for greater than 3 months. Many insurers have adopted these rules, without evidence in post-operative patients.

- We hypothesize that routine post-operative supplementation will enhance patients recovery and quality of life, by increasing the time of adequate nutrition.

Specific Aim 2: To determine the occurrence of common complications and readmissions post-operatively between patients who are routinely discharged with tube feeding and those that are not. If patients are not discharged with tube feeds, they must obtain all of their nutrition by mouth, which may be difficult in the early post-operative period.

- We hypothesize that routine use of tube feeding may reduce the occurrence of complications.

The secondary aims of this randomized clinical trial are:

- To compare costs of care between groups.
- To assess how length of stay (LOS) and readmission rates are affected by routine use of tube feeding, as well as costs of care.
- Rates of occurrence of tube feeding or jejunal tube-specific complications

## B. BACKGROUND AND SIGNIFICANCE

Nutritional support is taking on an increasing focus in peri-operative surgical care. It is particularly important in esophageal resection, which is a high-risk operation in a patient population whose pre-operative condition may be reduced due to pre-operative chemo- and radio-therapy, as well as dysphagia from the cancer. Post-operatively, patients are routinely cleared to take nutrition by mouth once an esophagram is done post-operative day 7 and shows no abnormality.

Tube feeding should be at goal by day 7, but is discontinued once patients are discharged, as long as they are able to eat, i.e., do not have evidence of anastomotic leak or other serious complications. The amount patients are able to eat is frequently variable, and is not well recorded prior to or after discharge. There may be a dip in calories consumed, which if severe, will lead to readmission for

hydration, failure to thrive, or possibly the development of a post-operative complication.

Currently all patients are discharged with the jejunal feeding tube placed at the operation, just in case they are unable to eat post-operatively due to an unforeseen complication. Since many insurers and Medicare require patients to pay for tube feeding needed for less than three months (~\$800/month and up, plus the services of a home health nurse), we do not routinely require patients use the feeding tube once discharged.

For esophagectomy specifically, and upper gastro-intestinal surgery in general, there is very limited literature looking at this question. Small randomized studies have not shown a benefit to routine tube feeding, although the numbers were very small, ranging from 12 to 70 in each group. Furthermore, the duration of tube feeding averaged 14 days, and even in the groups being fed enterally, were not meeting caloric needs in the period studied.

### **C. STUDY SCHEMA**

Patients will be evaluated for surgery by the study surgeons. Patients scheduled to undergo an elective esophagectomy and who meet inclusion criteria (See Section E.1) will be approached for enrollment. Written informed consent will be obtained from all enrolled patients (see Appendix B). Pre-operative Quality of Life Survey will be obtained using the EORTC QLQ-C30 (see attached). Patients will then be randomly assigned to either routine post-operative tube feeding for 1 month, or usual practice, tube feeding to continue in the hospital until the patient is taking adequate nutrition by mouth at POD#8, or upon discharge. Since this study cannot be blinded, patients that cannot take nutrition by mouth at POD#8, or are tube feeding dependent on discharge will not be included in analysis.

Figure 1. Illustrates the study design

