### **E.2. Exclusion Criteria**

- E.2.1 Emergent procedure.
- E.2.2 Less than 18 years of age.
- E.2.3 Inability to provide informed consent or to complete testing or data collection.
- E.2.4 Unwillingness to be randomized.
- E.2.5 Tube feeding dependent on discharge.

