## **F. RANDOMIZATION AND MASKING**

Randomization envelopes will be created at the start of the study. Each envelope will be opened prior to discharge or at POD#8 if patients are able to take adequate nutrition by mouth, to determine if post-operative tube feeding will be continued or not.

By consenting to the study, patients agree to continue tube feeding for at least 50% of caloric needs for 1 month post-operatively. Cross-over after randomization will be permitted for patient condition, although once randomized, patients will be analyzed by the original group.

- A copy of the signed research consent form must be included in the patient's hospital chart.

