**Randomization:**

This study will randomize eligible patients to receive post-operative tube feeding for 1 month or standard post-operative care in a one-to-one fashion. Patients will be randomized using a blocked randomization technique in order to ensure equal sample sizes across groups. [name] – is this correct? The study statistician ([name]) will generate the randomization assignment table for the study's data manager. The investigators will call the data manager for the treatment assignment when a patient has been fully consented and is determined to be eligible for study enrollment.

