## L. DISCUSSION OF POTENTIAL LIMITATIONS IN STUDY DESIGN

A potential pitfall is that patients who consent to the study in the preoperatively, may not continue to meet eligibility criteria prior to discharge or at POD#8 because they are not able to take adequate nutrition by mouth, thus excluding the patient from randomization and further participation in the trial.

Another potential pitfall is that patients who randomize to have their tube feeding discontinued at discharge may (due to patient condition) require tube feedings to be resumed to supplement nutritional needs. Cross-over after randomization will be permitted for patient condition, although once randomized, patients will be analyzed by the original group.

[name], how do we construct randomization schema and power analysis to account for these limitations?

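### A patient randomised at POD#8 and tube feeding dependent at a later discharge is dropped from analysis by Section C but kept by Sections F and L

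*Combined protocol and SAP*

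**What the plan says.** Section C excludes from analysis patients who cannot take nutrition by mouth at POD#8, "or are tube feeding dependent on discharge will not be included in analysis". Section E.2.5 lists the same discharge status as an exclusion criterion: "Tube feeding dependent on discharge". Section K defines evaluable patients through the exclusion criteria of Section E.2, which include E.2.5.

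Section F sets the time of randomisation: "Each envelope will be opened prior to discharge or at POD#8 if patients are able to take adequate nutrition by mouth". It permits cross-over for patient condition and adds that "once randomized, patients will be analyzed by the original group". Section L repeats that rule.

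Other places bear on timing. In Section C, straight after the pre-operative survey, we read "Patients will then be randomly assigned to either routine post-operative tube feeding for 1 month". The Randomization paragraph of Section J gives the assignment "when a patient has been fully consented and is determined to be eligible for study enrollment", without naming a time. Section L says that losing eligibility through inadequate oral intake before discharge or at POD#8 has the effect of "thus excluding the patient from randomization and further participation in the trial". The table in Section N places randomisation in the inpatient post-operative column, and its footnote puts the check of continued eligibility before randomisation.

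**The concern.** The Section C rule depends on a status observed at discharge, whereas Section F allows randomisation before discharge. For a patient who changes status in between, one rule removes the patient from analysis and the other keeps the patient. The analyst would have to choose, possibly after seeing outcomes.

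If Section C were followed, the removal would take place after randomisation with the arm known, since Section C itself says the study cannot be blinded. It would also be related to outcome. Section B treats being able to eat as the absence of anastomotic leak or other serious complication, and Section D names anastomotic leak within the Aim 2 primary outcome. Removal could differ between arms as well: tube feeding dependence is not defined, and one arm is assigned to continue tube feeding. Telling dependence from assigned feeding at discharge is therefore a judgement made with knowledge of the arm. Either aim could be biased, in either direction.

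**Working it through.** **Consistency check.** Follow one patient through the sections.

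1. Oral intake is adequate at POD#8, so the envelope is opened (Section F).
2. The patient stays in hospital and deteriorates.
3. At discharge the patient is tube feeding dependent.
4. Section C takes the patient out of the analysis, and under E.2.5 and Section K the patient is not evaluable.
5. Sections F and L keep the patient in the assigned group.

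Steps 4 and 5 cannot both be carried out. The eligibility check in Sections J, L and N does not resolve this, because a check at POD#8 cannot observe status at a later discharge. In addition, if the order of the Section C narrative were taken literally, with assignment right after the pre-operative survey, its POD#8 oral-intake exclusion would also fall after randomisation.

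**Size.** There is no figure in the plan to reproduce: it gives no complication risk, no frequency for this situation, and only a placeholder for the sample size. The following is an illustration on assumed inputs.

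- True complication risk: 30% in both arms (no treatment effect).
- Share of an arm removed: d = 1%, 2%, 5% or 10%.
- Risk among those removed: r = 80% or 50%.

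Observed risk in an arm after removal = (0.30 − d·r)/(1 − d). Differences are feeding minus usual care.

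Example, removal from usual care only with d = 0.05 and r = 0.80: (0.30 − 0.04)/0.95 = 0.2737, so the difference is 30.00 − 27.37 = +2.63 points.

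| Share removed | Usual care only, r = 80%: observed risk | Difference (points) | Usual care only, r = 50%: observed risk | Difference (points) | Both arms, r = 80% usual care and 50% feeding: difference (points) |
|---|---|---|---|---|---|
| 1% | 0.2949 | +0.51 | 0.2980 | +0.20 | +0.30 |
| 2% | 0.2898 | +1.02 | 0.2959 | +0.41 | +0.61 |
| 5% | 0.2737 | +2.63 | 0.2895 | +1.05 | +1.58 |
| 10% | 0.2444 | +5.56 | 0.2778 | +2.22 | +3.33 |

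Removal from the feeding arm only gives the same sizes with a negative sign. Swapping the two risks in the last column also reverses its sign. Equal shares with equal risk give a difference of 0. Equal shares alone do not protect, as the last column shows.

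No corresponding calculation was made for quality of life, the Aim 1 primary outcome.

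**The case against.** The strongest reply is that Section C was never meant to act after randomisation. Sections C, F and L use the same pair of time points, POD#8 and discharge. Section L speaks of exclusion from randomisation, and Section N puts the eligibility check first. On that reading Section C describes consented patients who fail the check and are never randomised, and E.2.5 is an eligibility criterion, not an analysis-set rule. For patients already randomised, the more specific rule appears twice: "Cross-over after randomization will be permitted for patient condition, although once randomized, patients will be analyzed by the original group".

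This is probably what the authors intended, and it settles the matter for patients who fail before the envelope is opened. It does not cover the patient randomised at POD#8 and discharged later. No sentence limits the Section C discharge rule to patients not yet randomised, and that rule speaks of analysis, not of randomisation.

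Two further points stand. First, the group is likely to be small: Section F requires adequate oral intake before the envelope is opened, and Section B clears oral intake only after a normal day 7 esophagram. The 5% and 10% rows above are therefore less plausible than the 1% and 2% rows, and one-arm removal is the extreme case. Second, Sections F, L and N agree on in-hospital, post-operative randomisation, so the timing conflict comes only from the order of the Section C narrative; Section J is silent on time. Section L also ends with an open question about the randomisation scheme and power, so the authors knew that this area was unfinished.

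**Conclusion.** The contradiction is real and should be fixed. The plan yields two different analysis sets as soon as one such patient occurs, and one of them involves an unblinded, outcome-related exclusion after randomisation. The textual conflict is certain; its effect on the results is not. On the assumptions above, a subgroup of 1% to 2% moves the complication difference by about 1 point or less. Larger or more unequal removal could move it by several points, with a sign that cannot be predicted. The documents do not say how often the situation would arise.

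**What to change.** Change the wording so that the original-group rule covers everyone randomised:

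- **Section C:** state that *the oral-intake and tube-feeding-dependence exclusions apply only at the eligibility check immediately before the envelope is opened, and all randomised patients are analysed in their assigned group*.
- **Section E.2.5:** tie the criterion to *the pre-randomisation eligibility check* in place of discharge. State what counts as tube feeding dependence for this check; the content of that definition is for the clinical team.
- **Section K:** state that the definition of evaluable does not remove a randomised patient through E.2.5. The replacement of drop-outs and patients lost to follow-up in the same section also affects who is analysed and needs its own review.
- **Sections C and J (Randomization):** reconcile with Section F, so that one time of randomisation is given throughout and it follows the eligibility check.

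No new procedures are needed. The cost is that usual-care patients who become tube feeding dependent stay in and slightly dilute the contrast, as the existing cross-over policy already accepts. If a share d of that arm received the full effect of feeding, the observed difference would be (1 − d) of its size: 99%, 98%, 95% or 90% for assumed shares of 1%, 2%, 5% or 10%.

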### **D. OUTCOME MEASURES**

The primary outcome measure for specific aim 1 will be the quality of life and patient satisfaction as measured by post-operative survey instruments.

Secondary Outcomes for specific aim 1:

- Complications following surgery (jejunal tube)
- Length of stay
- Costs

The primary outcome for specific aim 2 will be the occurrence of post-operative complications such as: atrial fibrillation, delirium, anastomotic leak, pneumonia within the 30-day post-operative time frame.

Secondary Outcomes for specific aim 2:

- Readmission rates and costs of care.

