## **G. TREATMENTS**

### **G.1 Standardization of Intervention**

#### **All Procedures:**

1. The participating study surgeons have been trained in and regularly perform esophagectomies with jejunostomy tube placement.
2. The supervising study surgeon will be present for key portions of the procedure. Residents or fellows may participate in procedures as is standard.

3. Patients will undergo standardized preoperative and postoperative education.
4. Patients will undergo standard postoperative care specific to the procedure performed, including enteral tube feeding while in the hospital until adequate nutrition by mouth is tolerated.

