## **H. MEASUREMENT**

The assessment instruments that will be used for specific aim 1:

1. EORTC QLQ-C30, Quality of life in cancer patients

The complications assessment instruments that will be used for specific aim 2:

1. HUM00012731 data collected around the time of operation and post-operative visit.
2. Long-term data from HUM00012731

Patients will also be invited to enroll in the “Patient outcomes following esophagectomy for benign and malignant disease” HUM00012731, a study in which the PI ([name]) is also a co-investigator. To minimize patient burden, the baseline preoperative assessment and the evaluation for quality of life will be performed according to the protocol outlined in HUM00012731. Demographics and history forms HUM00012731 will only be administered once preoperatively. This data will then be shared to support the study aims of this protocol to minimize patient inconvenience. In the event, that a patient does not wish to be co-enrolled in HUM00012731, the attached forms (EORTC QLQ-C30 and Demographics and history forms HUM00012731) will be administered by the Thoracic Surgery Clinical Coordinator, who will be trained and added to the HUM000XXXXX study protocol, at the scheduled time points outlined in Section N.

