#### **b. Specific Aim 2**

Occurrence and severity of complications will be recorded by HUM00012731. Patients will be assessed at discharge and return visits. Adverse events following surgery (e.g, pneumonia, DVT, PE, anastomotic leak, atrial fibrillation, delirium, etc.) will be identified prospectively by the study team

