## **H.3 Schedule of Measurements**

Section N details the schedule of measurements. Data will be collected preoperatively at the initial screening visit, during the perioperative period, at the follow-up appointment (2 weeks following discharge), and at 1 month, 3 months, and 6 months (by telephone or mail).

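### The Aim 2 primary outcome counts complications from surgery to day 30, but feeding cannot differ between arms until POD#8 or discharge, so events that allocation cannot affect are counted and power is lost

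*Combined protocol and SAP*

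**What the plan says.** Section D gives the primary outcome for Specific Aim 2 as "the occurrence of post-operative complications such as: atrial fibrillation, delirium, anastomotic leak, pneumonia within the 30-day post-operative time frame". The window is anchored to the operation, and no section restricts it to events that begin after randomisation.

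Allocation comes later. Section F states: "Each envelope will be opened prior to discharge or at POD#8 if patients are able to take adequate nutrition by mouth". Table 1 in section N puts randomisation in the inpatient post-operative column, after a second eligibility check. Until then feeding is common to everyone: section G.1 prescribes standard care "including enteral tube feeding while in the hospital until adequate nutrition by mouth is tolerated". Section A frames Aim 2 as a comparison "between patients who are routinely discharged with tube feeding and those that are not".

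On data collection, section H takes complications from "HUM00012731 data collected around the time of operation and post-operative visit". Section H.1(b) says: "Adverse events following surgery (e.g, pneumonia, DVT, PE, anastomotic leak, atrial fibrillation, delirium, etc.) will be identified prospectively by the study team", with assessment at discharge and return visits. Section H.3 says: "Data will be collected preoperatively at the initial screening visit, during the perioperative period". In Table 1, however, the Adverse Events row has no inpatient mark, and section J compares calories, not complications, for Aim 2.

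**The concern.** The outcome window opens about a week or more before the two groups can receive different feeding. A complication that starts in that interval cannot be caused or prevented by the assigned arm. Randomisation spreads such events evenly in expectation, so they add no systematic difference and do not raise the type I error.

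They do dilute the comparison. In an any-complication or single-complication analysis, a patient who already has an early event counts as a case whatever happens later. The risk difference shrinks and the risk ratio moves towards 1. If events are counted rather than patients, the absolute difference is unchanged but its variance rises. Either way, a real effect on later complications becomes easier to miss. The contrast in section A concerns what happens after allocation, so the window also does not match the trial's own question.

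**Working it through.** **No figure to reproduce.** Section K leaves the sample size as a placeholder. Section J gives no alpha, power, event rate or complication test. All rates below are therefore assumptions, with two-sided alpha 0.05, 80% power and 1:1 allocation.

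**Share of the window.** With randomisation on day 8, 8/30 = 27% of the window precedes any difference in feeding. This is a share of time, not of events.

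**Dilution.** Let q be the proportion of randomised patients with a listed complication before randomisation (the same in both arms), and p1, p2 the risks afterwards. With early and later events independent:

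- risk as worded = 1 − (1 − q)(1 − p)
- risk difference = (1 − q)(p1 − p2)
- n per arm = (1.960 + 0.842)² × [a(1 − a) + b(1 − b)] / (a − b)², where a and b are the diluted risks

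Worked line for 30% v 20% with q = 10%: a = 1 − 0.9 × 0.7 = 0.37 and b = 1 − 0.9 × 0.8 = 0.28. The difference is 0.09, and n = 7.849 × (0.2331 + 0.2016)/0.0081, which rounds up to 422, against 291 at q = 0.

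Any-complication outcome, later risks 30% v 20%:

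| q | Risks compared | Difference (points) | n per arm | Ratio to 291 | Power at 291 |
|---|---|---|---|---|---|
| 0 | 30.0% v 20.0% | 10.0 | 291 | 1.00 | 80% |
| 2% | 31.4% v 21.6% | 9.8 | 315 | 1.08 | 77% |
| 5% | 33.5% v 24.0% | 9.5 | 353 | 1.21 | 72% |
| 10% | 37.0% v 28.0% | 9.0 | 422 | 1.45 | 64% |
| 20% | 44.0% v 36.0% | 8.0 | 585 | 2.01 | 51% |

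**Other assumed settings.**

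- *Any complication, 15% v 7.5%.* 275 per arm at q = 0. For q = 2/5/10/20%: 326/406/550/894, ratios 1.19/1.48/2.00/3.25.
- *One complication alone, 6% v 3%.* 746 per arm at q = 0. For q = 1/2/5%: 914/1086/1623, ratios 1.23/1.46/2.18.
- *Event counts, Poisson, means 0.30 v 0.20.* n = 7.849 × (sum of the two means)/0.10², giving 393 with no early events. Adding 0.02/0.05/0.10/0.20 early events per patient to both arms gives 424/471/550/707, ratios 1.08/1.20/1.40/1.80.

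**Checks.** If patients with an early event have twice the later risk, with overall later risks held at 30% v 20%, q = 2/5/10/20% needs 324/380/493/817 per arm (ratios 1.11/1.31/1.69/2.81). Independence is thus the milder assumption. A pooled-variance formula for 30% v 20% gives 294 per arm at q = 0, with power at that size of 65% for q = 10% and 51% for q = 20%, in line with the table.

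**The case against.** **The eligibility check may remove most early events.** Section L describes patients who cannot eat adequately as failing the check, "thus excluding the patient from randomization and further participation in the trial". Section B ties oral intake to a normal esophagram on day 7 and describes patients able to eat as having no leak or other serious complication. An early leak is therefore largely screened out, and q could be small; at q = 2% in the main illustration, power falls only from 80% to 77%. This stands as a limit on size. It does not remove the problem: a patient with early atrial fibrillation, delirium or pneumonia who eats by POD#8 can still be randomised, and those are three of the four named complications.

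**Early events may never reach the analysis.** Table 1 has no inpatient Adverse Events mark, and section A could be read as a post-discharge comparison. But sections H, H.1(b) and H.3 collect perioperative data and assess patients at discharge, and the section D wording includes early events. The documents conflict, so this objection supports reconciling them rather than leaving the wording alone.

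**Power presupposes a powered test.** Section J plans no complication comparison and section K has no sample size. Those gaps are more basic. They are also a reason to settle the outcome now, before the missing calculation is done.

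**Randomisation may be earlier.** The sentence order in section C suggests assignment soon after consent. Its usual-practice arm is still tube fed until POD#8 or discharge, so feeding would not differ sooner. The Randomization paragraph in section J can be read consistently with section F if eligibility there includes criterion E.2.5.

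**Conclusion.** The concern holds. Followed as written, section D counts complications that allocation cannot affect, and this dilutes any effect of feeding after discharge. The direction follows from sections D, F, G.1 and N alone and does not depend on assumed rates.

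The size cannot be fixed from the documents. Over the any-complication settings assumed here, with 2% to 20% of randomised patients having an early event, the required sample size rises by a factor of about 1.1 to 3.3. The lower end applies if few early events pass the eligibility check. The finding concerns lost power, not bias or false positives. The change should be made, because this is a primary outcome and the loss is avoidable.

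**What to change.** 1. In section D, define the Aim 2 primary outcome as new onset of a listed complication after randomisation, over a stated window. The window may end at post-operative day 30, or run for a fixed number of days from randomisation.
2. Close the list of complications. Section D's list is open, and section H.1(b) adds DVT, PE and an unspecified remainder.
3. State one time of randomisation, and word section C and the Randomization paragraph of section J to agree with sections F, L and N.
4. Treat complications before randomisation as a baseline characteristic, and report counts from surgery descriptively.
5. Record onset dates, and reconcile the Adverse Events row of Table 1 with sections H, H.1(b) and H.3.
6. Name the complication comparison in section J, and base the sample size on this outcome.

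The cost is mainly wording, one Table 1 mark, and an onset-date field if the HUM00012731 forms, which are not in the documents, lack one. Table 1 already schedules adverse events at 2 weeks and at 1, 3 and 6 months, so with onset dates either window can be collected.

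There are trade-offs. Fewer events will be counted. A window ending on post-operative day 30 gives unequal follow-up: randomisation on day 8, 14 or 20 leaves 22, 16 or 10 days, and the documents give no distribution of that day. A fixed window from randomisation avoids this but departs from the 30-day post-operative frame in section D.
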